| 12.6 | ECOG Status..... | 20 |
| 12.7 | Physical Examination | 20 |
| 13.0 | Interim Analysis..... | 20 |
| 14.0 | Changes to Planned Methodology | 20 |
| 15.0 | Tables, Figures and Listings | 22 |
| 15.1 | List of Tables..... | 22 |
| 15.2 | List of Figures..... | 23 |
| 15.3 | List of Listings..... | 23 |

Abbreviations

| Abbreviation | Meaning |
|--------------|--|
| ADV | Adenoviral vector shedding |
| AE | Adverse Event |
| ACEV | Activity Evaluable Population |
| ATC | Anatomical Therapeutic Chemical |
| bpm | Beats per minute |
| BMI | Body mass index |
| BRAF | Human gene that makes a protein called B-Raf |
| cm | Centimeter |
| CR | Complete Response |
| CTCAE | NCI Common Terminology Criteria for Adverse Events |
| CTL | Cytotoxic T Lymphocytes |
| DLT | Dose-limiting Toxicity |
| ECG | Electrocardiogram |
| FNA | Fine Needle Aspirate |
| GGT | Gamma Glutamyl Transferase |
| Hgb | Hemoglobin |
| INXN-1001 | INXN-1001 (Oral Activator Ligand) |
| INXN-2001 | INXN-2001 (Ad-RTS-hIL-12) |
| kg | Kilogram |
| KM | Kaplan-Meier |
| lb | Imperial pounds (weight) |
| MedDRA | Medical Dictionary for Regulatory Activities |
| mg | Milligram |
| MTD | Maximum Tolerated Dose |
| PB | Punch Biopsy |
| PBMC | Peripheral Blood Mononuclear Cells |
| PD | Progressive Disease |
| PFS | Progression-free Survival |
| PK | Pharmacokinetic |
| PR | Interval measured from the beginning of the P wave to the beginning of the QRS complex |
| PR | Partial Response |
| PT | Preferred term |
| PTSA | Post Treatment Safety Assessment |
| QRS | Complex containing Q wave, R wave and S wave |
| QT | Interval between start of the Q wave and the end of the T wave |
| RBC | Red Blood Cell Count |
| RECIST | Response Evaluation Criteria In Solid Tumors |

| Abbreviation | Meaning |
|--------------|----------------------------------|
| SAE | Serious Adverse Event |
| SAF | Safety Population |
| SAP | Statistical Analysis Plan |
| SAS | Statistical Analysis System |
| SD | Standard Deviation |
| SD | Stable Disease |
| SOC | System Organ Class |
| SRC | Safety Review Committee |
| TEAE | Treatment-Emergent Adverse Event |
| Tregs | T-regulatory cells |
| vp | Viral particles |
| WHO | World Health Organization |

1.0 Version Control

This Statistical Analysis Plan (SAP) is based on the protocol ATI001-101 Amendment 7, issued 29 April 2013.

The planned enrollment for this study was approximately 30 patients (3 patients per dose level cohort) in Phase I and approximately 15 patients enrolled in Phase II at a single dose level at or below the Maximum Tolerated Dose (MTD).

Enrollment proceeded as follows:

Three patients were treated in cohort 1 at 5mg QD of INXN-1001, three patients treated in cohort 2 at 20mg QD, three patients treated in cohort 3 at 100mg QD, and 4 patients were treated at 160mg QD.

Four patients were treated in the expansion cohort (Phase II) at 160mg QD and four at 160mg QOD. A decision was then taken by the SRC to enroll into the expansion cohort at a reduced dose of INXN-1001; a further three patients were treated at 120mg QOD and two patients were treated at 80mg QOD, due to dose limiting toxicities (DLTs) occurring on the 160mg QOD and the 120mg QOD dose cohorts.

Further details of subject enrollment will be presented in the Clinical Study Report (CSR). This SAP describes the changes to the planned analysis along with the modified analysis for the amended design.

This SAP refers to the final analysis of the data. Pharmacokinetic (PK) data presentations and analysis will be performed by ZIOPHARM. No further details of PK analysis will be included in this SAP, with the exception of listing eCRF data.

2.0 Study Rationale

This study was designed to assess the safety, objective response rate and immunological and biological effects of intratumoral injections of INXN-2001 in combination with escalating dose levels of oral INXN-1001.

3.0 Objectives

3.1 Primary Objectives

The primary objective of this trial was to evaluate the safety and tolerability of intratumoral injections of INXN-2001 (Ad-RTS-hIL-12) in combination with INXN-1001 (activator ligand) in patients with unresectable Stage III or IV melanoma.

3.2 Secondary Objectives

The following secondary objectives were to be evaluated in the trial:

- To inform the selection of an INXN-1001 dose(s) and regimen for further study in combination with INXN-2001.

- To assess preliminary anti-tumor activity according to Response Evaluation Criteria In Solid Tumors (RECIST) 1.1 criteria.
- To assess anti-tumor response based on total measurable tumor burden.
- To evaluate the immunological effect of study treatment in terms of cellular and humoral immune responses, as well as other biological activities in the injected tumor(s), tumor-involved draining lymph nodes (if accessible) and in the peripheral circulation.
- To evaluate the extent of the uptake of INXN-2001 into tumor cells and tumor-infiltrating immune cells, and to assess adenoviral vector shedding in body fluids.
- To assess the pharmacokinetics (PK) of INXN-1001 in patients with unresectable stage III or IV melanoma.

4.0 Study Design

4.1 Endpoints

Safety Evaluations

Safety parameters were to include serious adverse events (SAEs), adverse events (AEs), physical examinations, electrocardiograms (ECGs), vital signs, clinical laboratory evaluations, medical history, and prior/concomitant medications.

Efficacy Evaluations

Efficacy was to be evaluated as the objective tumor response according to RECIST v1.1 guidelines. Additional assessment of anti-tumor activity was to be explored based on total measurable tumor burden.

Pharmacodynamic Evaluation

Immunological and biological markers of response were to include examinations of tumor biopsy samples, cytokine levels, peripheral blood mononuclear cells (PBMC) and antibody responses.

4.2 Overall Study Design

This was a single-arm, open label, Phase I/II dose escalation study of intratumoral injections of INXN-2001 and oral INXN-1001 in patients with unresectable Stage III or IV melanoma.

Approximately 30 patients (3 patients per dose level cohort) in Phase I and approximately 15 patients were to be enrolled in Phase II at a single dose level at or below the Maximum Tolerated Dose (MTD)).

Concurrent INXN-2001 and INXN-1001 dosing will be referred to as "study treatment" throughout this SAP.

This study is multi-center (approximately 8 to 12 centers).

Phase I

Phase I comprised of four planned sequential dose escalation cohorts of INXN-1001 in combination with a fixed dose of INXN-2001. Patient enrollment and dose escalation was to proceed according to a standard 3+3 design. Each patient was to be treated for up to 6 treatment cycles, each of 21 days in duration. In each cycle, patients were to be treated with one intratumoral injection of INXN-2001 in combination with 7 oral daily doses of INXN-1001 (Table 1).

Table 1: Study Design

| Study Part | Cohorts | Dose Regimen |
|------------|-----------------|---|
| Phase I | Dose Escalation | INXN-2001: [REDACTED] INXN-1001: 5, 20, 100, 160 mg |
| Phase II | Group 1 | INXN-2001: [REDACTED] INXN-1001: 160 mg daily for 7 consecutive days; 21-day cycle |
| | Group 2 | INXN-2001: [REDACTED] INXN-1001: 160 mg every other day for 14 days; 28-day cycle |

This study was to explore four INXN-1001 dose cohorts of 5 mg, 20 mg, 100 mg and 160 mg daily.

Phase II

Approximately 15 patients were to be enrolled in Phase II at or below the MTD. Phase II of the study was to include two groups of patients. Patients enrolled in Phase II of the study under Amendment 6 or prior were to be enrolled into Group 1; patients enrolled under Amendment 7 or later were to be enrolled into Group 2.

For Group 1, in each of six 21-day cycles, the patients were to receive one intratumoral injection of INXN-2001 in combination with oral daily doses of INXN-1001 given at 160 mg for 7 consecutive days at the beginning of the 21-day cycle.

For Group 2, in each of six 28-day cycles, the patients were to receive one intratumoral injection of INXN-2001 in combination with oral doses of INXN-1001 given at 160 mg administered every other day for 14 days at the beginning of the 28-day cycle.

Full details of the study design can be found in the protocol. Following changes to patient enrollment, the final study is shown in Table 2.

Table 2: Final Study Design

| Study Part | Cohorts | Dose Regimen |
|------------|-----------------|---|
| Phase I | Dose Escalation | INXXN-2001: [REDACTED] INXXN-1001: 5, 20, 100, 160 mg |
| Phase II | Group 1 | INXXN-2001: [REDACTED] INXXN-1001: 160 mg daily for 7 consecutive days; 21-day cycle |
| | Group 2 | INXXN-2001: [REDACTED] INXXN-1001: 160 mg every other day for 14 days; 28-day cycle 120 mg every other day for 14 days; 28-day cycle 80 mg every other day for 14 days; 28-day cycle |

4.3 Safety Review Committee (SRC)

A SRC comprised of the Medical Monitor, Principal Investigators, and sponsor representatives, were convened to review safety information and to decide upon dose escalation and further patient enrollment.

In Phase I, following a cohort review, the SRC could recommend proceeding with enrollment in the next dose cohort, enrolling additional patients in the current cohort, dropping back to a lower cohort, exploring an alternate dose level, or not enrolling any additional patients. The dose escalation and enrollment guidelines and study stopping rules outlined in the protocol (Sections 6.2.6 and 6.2.7) were to be used as the basis for these assessments.

In Phase II, Group 2, the DLT definitions in the protocol (Section 6.2.4) were to be utilized along with the criteria for de-escalation. The SRC could recommend a dose reduction for patients in Group 2 if one or more DLTs are observed.

4.4 Design Post Safety Review Committee Decision

Dose escalations in Phase I occurred as detailed in the protocol. For Phase II of the study, four patients were enrolled on 160mg QD and four patients on 160mg QOD; the decision was then taken to enroll patients on a reduced dose of 120mg QOD. The dose was then further reduced to 80mg QOD. The decision to reduce the dosing was due to DLTs occurring on the 160mg QOD and the 120mg QOD dose cohorts respectively.

5.0 Study Procedures

Various procedures will be performed during the study. The schedule of assessments is detailed in the protocol.

6.0 Patient Disposition

6.1 Sample Size

No formal sample-size estimation was performed.

Thirteen patients were treated in Phase I and 13 patients were treated in Phase II.

7.0 Protocol Deviations

Protocol deviations are defined as those deviations from the study protocol that may have the ability to impact the results.

No patient will be removed from any analysis population because of a protocol deviation. Protocol deviations were partially collected on the CRF. A further review of the data will be conducted to identify any of the following:

- Deviation from inclusion/exclusion criteria
- Withdrawal criteria met during the study but patient was not withdrawn
- Use of prohibited concomitant medications.

Where possible the first two items will be checked programmatically. For prohibited medications, a spreadsheet of the coded terms will be provided for the sponsor to review.

All protocol deviations including those not databased will be listed.

8.0 Analysis Populations

The target population for this study is adult patients with unresectable Stage III or IV melanoma for which there is no alternative curative therapy.

For the analysis, two populations will be used: a Safety population (SAF) and an Activity Evaluable population (ACEV).

8.1 Safety Population (SAF)

The Safety population is defined as all patients who receive at least one INXN-1001 capsule or, in the event an injection of INXN-2001 is administered before an INXN-1001 capsule is taken, at least one injection of INXN-2001.

The safety population will be used for the analysis of safety data based on the actual initial dose of INXN-1001 received.

8.2 Activity Evaluable Population (ACEV)

The Activity Evaluable population is defined as all SAF patients who receive at least one dose of INXN-2001 and INXN-1001 and have at least one post-screening response evaluation. The ACEV population is the primary population for the analysis of efficacy data.

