11.0 Efficacy

Patients with measurable disease will have tumor dimensions measured according to Response Evaluation Criteria in Solid Tumors (RECIST) version 1.1 at Screening

and at the each cycle up to cycle 6 during the study and 8-10 weeks after follow-up if the patient is without objective evidence of disease progression at the Follow-Up Tumor Assessment visit. The investigator will evaluate each patient for response to therapy according to RECIST v1.1 guidelines. For each patient, disease sites are to be assessed throughout the study using the same method(s) of assessment used at screening.

Additional assessment of anti-tumor activity will be explored based on total measurable burden.

Immunological and biological markers of response will include examinations of tumor biopsy samples, cytokine levels, peripheral blood mononuclear cells (PBMC) and antibody responses.

All summaries will be performed on the ACEV population and based on the dose of INXN-1001 received.

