11.1.2 Progression-free Survival

Progression free survival is the time in days from the first dose of INXN-1001 to the first assessment on which the overall response is reported as disease progression or death due to any cause (whichever is first) + 1 day. Patients withdrawing from the study will be censored at their last non-progressive disease response assessment. If a patient does not have a disease response assessment, the patient will be censored on the date of the first treatment as described above.

Progression-free survival and censoring information will be listed.

PFS times will be summarized using Kaplan-Meier methods. The median, 25th and 75th percentiles will be calculated. Kaplan-Meier plots will not be presented.

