14.0 Changes to Planned Methodology

The following changes will be made to the planned analysis based on the final number of enrolled subjects:

Section 10.3.3 of the Protocol states that following completion of the study, best response will be determined for each subject in accordance with RECIST v.1.1 guidelines and the objective response rate presented for each dose cohort. Progression-free survival and durability of response will be determined using Kaplan-Meier methodology.

Objective response, BOR and PFS will be determined and listed for each individual subject. Additionally BOR and PFS will be tabulated. Objective response rate and duration of response will not be calculated.

Section 10.3.3 of the Protocol also states that as a supplement to the standard RECIST v1.1 guidelines established to evaluate anti-tumor responses to chemotherapeutic agents, the sponsor will be analyzing anti-tumor response by assessing total tumor burden over time. Tumor burden activity was not collected and as such no summaries will be included for this data.

Section 10.3.3 of the Protocol also states that at each time point, the change in immunologic response (CTL and Treg frequency in blood) from baseline and from the preceding time point will be correlated with the INXN-1001 dosage level. In addition, tumor punch biopsies or FNAs will be examined for genomic changes due to IL-12 expression, presence of injected adenovirus and CTL frequency, Treg and MDSC frequency, and other immunological markers. The change in each measure from baseline and from the preceding biopsy will be correlated with the INXN-1001 dose used in the each cohort.

Immunologic and biological response marker data will be listed only.

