15.1 List of Tables

| Table Number | Table Title | Population |
|----------------|--|-------------------------------|
| Table 14.1.1 | Patient Disposition | Safety Population |
| Table 14.1.2 | Protocol Deviations | Safety Population |
| Table 14.1.3 | Demography | Safety Population |
| Table 14.1.4 | Medical History | Safety Population |
| Table 14.1.5 | Oncology History | Safety Population |
| Table 14.1.6 | Oncology History – Time Since Diagnosis, Disease Status and Staging | Safety Population |
| Table 14.1.7 | Previous Medications | Safety Population |
| Table 14.1.8 | Concomitant Medications | Safety Population |
| Table 14.1.9 | Prior Cancer Treatment | Safety Population |
| Table 14.2.1 | Best Overall Response | Activity Evaluable Population |
| Table 14.2.2 | Progression-free Survival (Kaplan-Meier Analysis) | Activity Evaluable Population |
| Table 14.3.1 | Exposure | Safety Population |
| Table 14.3.2.1 | Overall Adverse Event Summary | Safety Population |
| Table 14.3.2.2 | Adverse Events by System Organ Class and Preferred Term | Safety Population |
| Table 14.3.2.3 | Treatment Emergent Adverse Events by System Organ Class and Preferred Term | Safety Population |

| Table Number | Table Title | Population |
|-----------------|---|-------------------|
| Table 14.3.2.4 | Drug-Related Treatment Emergent Adverse Events by System Organ Class and Preferred Term | Safety Population |
| Table 14.3.2.5 | Serious Adverse Events by System Organ Class and Preferred Term | Safety Population |
| Table 14.3.2.6 | Drug-Related Serious Adverse Events by System Organ Class, Preferred Term | Safety Population |
| Table 14.3.2.7 | CTC Grade 3 or greater Adverse Events by System Organ Class, Preferred Term | Safety Population |
| Table 14.3.2.8 | Drug-Related CTC Grade 3 or Greater Adverse Events by System Organ Class and Preferred Term | Safety Population |
| Table 14.3.2.9 | Adverse Events Leading to Discontinuation by System Organ Class and Preferred Term | Safety Population |
| Table 14.3.2.10 | Summary of Injection Site Reactions | Safety Population |
| Table 14.3.2.11 | Summary of Injection Site Reactions by Type and Severity | Safety Population |
| Table 14.3.2.12 | Summary of Injection Site Reactions by Type and Relationship | Safety Population |
| Table 14.3.3.1 | Shift from Baseline to Worst Post-Baseline Value (Low/High) for Clinical Chemistry Parameters | Safety Population |

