15.3 List of Listings

Listings will be sorted by patient number within Phase, group (for Phase II patients) and dose cohort.

| Listing Number | Listing Title | Population |
|-----------------------|---|-------------------|
| Listing 16.2.1.1 | Patient Disposition | Safety Population |
| Listing 16.2.1.2 | Inclusion and Exclusion Criteria | Safety Population |
| Listing 16.2.1.3 | Eligibility | Safety Population |
| Listing 16.2.2 | Protocol Deviations | Safety Population |
| Listing 16.2.3 | Population Allocation | Safety Population |
| Listing 16.2.4.1 | Demography and Baseline Characteristics | Safety Population |
| Listing 16.2.4.2 | Medical History | Safety Population |
| Listing 16.2.4.3 | Oncology History | Safety Population |
| Listing 16.2.4.4 | Prior Cancer Therapy | Safety Population |
| Listing 16.2.4.5 | Prior Medications | Safety Population |
| Listing 16.2.4.6 | Concomitant Medications | Safety Population |
| Listing 16.2.5.1 | Study Drug Administration | Safety Population |
| Listing 16.2.5.2 | Drug Dosing Schedule | Safety Population |
| Listing 16.2.5.3 | Overall Study Drug Exposure | Safety Population |
| Listing 16.2.5.4 | Pharmacokinetic Sampling | Safety Population |
| Listing 16.2.6.1 | Tumor Assessments | Safety Population |
| Listing 16.2.6.2 | Overall Tumor Assessments | Safety Population |
| Listing 16.2.6.3 | Best Overall Response and Progression-free Survival | Safety Population |
| Listing 16.2.6.4 | PBMC | Safety Population |
| Listing 16.2.6.5 | Serum Antibody Responses | Safety Population |
| Listing 16.2.6.6 | Cytokine Profiling Responses | Safety Population |
| Listing 16.2.6.7 | Serum Tryptase Responses | Safety Population |
| Listing 16.2.6.8 | T cells | Safety Population |
| Listing 16.2.6.9 | NK cells | Safety Population |
| Listing 16.2.6.10 | T-regulatory (Tregs) | Safety Population |
| Listing 16.2.6.11 | Adenoviral Vector Shedding | Safety Population |
| Listing 16.2.7.1 | Adverse Events | Safety Population |
| Listing 16.2.7.2 | Treatment Emergent Adverse Events | Safety Population |

| Listing Number | Listing Title | Population |
|-----------------------|---|-------------------|
| Listing 16.2.7.3 | Treatment Emergent Serious Adverse Events | Safety Population |
| Listing 16.2.7.4 | Treatment Emergent Adverse Events Related to Study Drug | Safety Population |
| Listing 16.2.7.5 | Treatment Emergent Adverse Events Leading to Withdrawal | Safety Population |

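### The BOR and Kaplan-Meier PFS tables use only response-evaluable patients, so a treated patient who dies before any evaluation is in neither, although the SAP counts that death as a PFS event

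*SAP*

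**What the plan says.** - **Population.** ACEV patients must have received both drugs and "have at least one post-screening response evaluation. The ACEV population is the primary population for the analysis of efficacy data" (SAP 8.2). Protocol 10.1.2 sets the same condition.
- **Where it is used.** SAP 11.0: "All summaries will be performed on the ACEV population". SAP 15.1 assigns Table 14.2.1 (BOR) and Table 14.2.2 (Kaplan-Meier PFS) to ACEV. No efficacy table uses the Safety population. SAP 14.0 confirms that these are the efficacy tables: "Additionally BOR and PFS will be tabulated. Objective response rate and duration of response will not be calculated".
- **PFS rules (SAP 11.1.2).** The event is "disease progression or death due to any cause (whichever is first". A later sentence reads: "If a patient does not have a disease response assessment, the patient will be censored on the date of the first treatment". On output: "The median, 25th and 75th percentiles will be calculated. Kaplan-Meier plots will not be presented".
- **Response rules.** SAP 11.1.1 counts patients who cannot be assessed as non-responders. Unevaluable is a BOR category in 11.1.1 and 11.1.4.
- **Listing.** Listing 16.2.6.3, "Best Overall Response and Progression-free Survival", is on the Safety population (SAP 15.3).
- **Layout.** SAP 9.0 summarizes by phase and dose cohort, with an overall column per phase, and plans no inference.

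**The concern.** The endpoint definition and the table population pull in opposite directions. Death is a PFS event, but a patient who dies before the first evaluation cannot enter the population on which PFS is tabulated. The rules for patients without an assessment (first-treatment censoring, non-responder status) cannot reach a never-evaluated patient in an ACEV table either; for that patient they operate only in the Safety-population listings.

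SAP 11.1.2 also does not say which rule wins for a patient who has no assessment and has died: the event definition or censoring at first treatment.

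At stake is whether the tabulated activity results describe all treated patients or only those who lived long enough to be evaluated. Cohorts hold 2 to 4 patients and PFS is shown only as percentiles without a curve, so one missing patient can move a tabulated figure visibly.

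**Working it through.** **1. Sizes.** There is no sample-size calculation to reproduce. SAP 1.0 gives Phase I cohorts 3 + 3 + 3 + 4 = 13 and Phase II cohorts 4 + 4 + 3 + 2 = 13, matching SAP 6.1 (26 in all). The number of patients without an evaluation, k, is not in the documents. Every k and event day below is assumed.

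**2. Window.** In the protocol the first scheduled on-treatment scan is in Cycle 3. With 21-day cycles (Appendix 5, Day 15) that is 2×21 + 15 = Day 57. With 28-day cycles (section 8.4.4, Day 13) it is 2×28 + 13 = Day 69. SAP 11.0 instead says each cycle, which would shorten the window. An assessment is also due at early withdrawal.

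**3. BOR share.** With r responders the share is r/n on all treated patients and r/(n−k) in ACEV. A living never-assessed patient counts in k too.
- n = 3, r = 1, k = 1: 1/3 = 33.3% against 1/2 = 50.0%.
- n = 4, r = 1, k = 1: 1/4 = 25.0% against 1/3 = 33.3%.
- n = 13, r = 2: 15.4% against 16.7%, 18.2% and 20.0% for k = 1, 2, 3.
- r = 0: 0% in both.

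**4. PFS curve.** Suppose all patients are followed to an event, one patient dies unassessed on day d, and m of the other n−1 patients are event-free at time t.
- Before d: all treated (m+1)/n, ACEV m/(n−1). ACEV is equal or lower.
- From d onward: all treated m/n, ACEV m/(n−1). ACEV is higher while m > 0.

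For a phase of 13 with no other event before the first evaluation, the all-treated estimate just before it is 12/13 = 92.3%, 11/13 = 84.6% or 10/13 = 76.9% for k = 1, 2, 3, against 100% in ACEV. A living never-assessed patient is censored at first treatment and does not change the curve.

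**5. Percentiles.** The 25th percentile is the first time S(t) falls below 0.75, or the midpoint to the next event if S(t) equals 0.75. The median uses 0.50 in the same way.

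| Cohort (events by day) | 25th percentile, all treated vs ACEV | Median, all treated vs ACEV |
|---|---|---|
| 3: death 30, progressions 57, 140 | 30 (S = 2/3) vs 57 (S = 1/2) | 57 vs (57+140)/2 = 98.5 |
| 4: death 30, progressions 57, 57, 140 | (30+57)/2 = 43.5 vs 57 | 57 vs 57 |
| 3: progression 20, death 30, progression 57 | 20 vs 20 | 30 vs (20+57)/2 = 38.5 |
| 4: progression 20, death 30, progressions 57, 140 | (20+30)/2 = 25 vs 20 | (30+57)/2 = 43.5 vs 57 |
| 2: progression 20, death 30 | 20 vs 20 | (20+30)/2 = 25 vs 20 |

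In a cohort of 2 to 4 where the death comes first, the 25th percentile rises. If another event comes first, it can be unchanged or fall.

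**6. Whole phase, simulated.** Assumptions: 13 patients on 21-day cycles, exponential times with a 90-day median, and k failures before Day 57 taken as deaths on their exact dates. All other failures are dated at the next scan: Day 57, 5×21 + 7 + 28 = Day 140, Day 175, then every 63 days. Average Kaplan-Meier medians, all treated to ACEV, were:
- k = 1: 134.5 to 143.1 days (+6%)
- k = 2: 133.3 to 150.8 days (+13%)
- k = 3: 131.3 to 158.7 days (+21%)

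Counting both this and a 28-day schedule, the median did not move in 72–80% of runs for k = 1 or 2, and in 47–60% for k = 3. Assumed medians of 60 to 120 days gave +6–11%, +11–22% and +18–34%. The model has no scans at early withdrawal, so it cannot show the falls in step 5. Phase II mixed the two cycle lengths (4 and 9 patients), so neither schedule fits it exactly.

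**The case against.** The case for leaving the plan alone is fair. The protocol itself names ACEV for efficacy (10.1.2, 10.3.3), and the SAP follows it. Activity is secondary and descriptive, and the MTD and recommended dose rest on DLTs. Entry requires an expected survival of at least 6 months, so k may well be zero. SAP 10.1 tabulates the size of each population. Listing 16.2.6.3 covers all treated patients, and SAP 11.1.4 presents death date, PFS and BOR per patient, so with 26 patients a reader can rebuild the all-treated result. SAP 15.0 produces tables only where data suffice. All of this stands and lowers the weight of the point. It does not make the two tables cover every treated patient.

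A reader might also infer more than the documents support:
- *That the bias always favours the treatment, or that the 25th percentile always changes.* Step 5 shows unchanged and falling percentiles when another event precedes the death.
- *That the patient disappears.* Other Safety-population outputs include the patient, such as Table 14.1.1 (disposition) and Listing 16.2.3 (population allocation). Adverse-event outputs do so too if the death is recorded as an AE outcome.
- *That an objective response rate is inflated.* SAP 14.0 drops that rate; only BOR shares are tabulated.
- *That the SAP censors such deaths.* The literal sentence permits it, but the event definition makes death the natural reading. This is a gap in wording.

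**Conclusion.** The point holds, as a minor one. Followed as written, the SAP omits from both efficacy tables any treated patient who dies unassessed, and omits from the BOR denominator any treated patient who is never assessed. With no such patient there is no effect. With one, the CR and PR shares rise or stay at 0, and PFS is overstated from the date of that death onward, possibly understated before it. The percentiles usually rise or stay the same: in a cohort of 3 with the death first, the 25th percentile could read 57 days instead of 30. In a phase of 13 with one or two such deaths, the median most often does not move. These sizes rest on assumed counts and event days. The window of 8 to 10 weeks rests on the protocol's Cycle 3 scan and is shorter if SAP 11.0's each-cycle schedule was followed.

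**What to change.** - Tabulate BOR and PFS also on the Safety population (all treated), by cohort and overall per phase, and keep the ACEV tables.
- In the Safety-population BOR table, show never-evaluated patients as unevaluable and use all treated patients as the denominator. This needs saying, because SAP 9.1 bases percentages on non-missing values and such patients could otherwise drop out.
- In SAP 11.1.2, state that death without a prior assessment is an event on the date of death, so first-treatment censoring applies only to patients with neither an assessment nor a death.

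The cost is a few sentences and two extra tables, with no new data. The figures may look slightly less favourable.
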